13.1.4. Key Secondary Efficacy Analyses

The key secondary efficacy endpoints will compare OCA to placebo on the following:

- Time to first occurrence of MELD score ≥ 15
- Time to liver transplant or death (all-cause)
- Change from Baseline in total bilirubin at end of study
- Change from Baseline in ALP at end of study

The key secondary efficacy analyses will compare randomized OCA to randomized placebo in ITT population with respect to the key secondary efficacy endpoints. Only adjudicated events will be included in time-to-event analyses. The comparison (hypothesis testing) will be conducted as specified in [Section 13.1.11](#) in a sequential closed testing gate-keeping procedure, provided that the primary efficacy endpoint comparison is statistically significant in favor of the

OCA treatment group. If the primary comparison is not statistically significant then comparison of the secondary endpoints will be considered as descriptive and exploratory. This procedure controls the study-wise type I error.

The 2 treatment groups will be compared using the same methodology as specified for the primary efficacy analysis ([Section 13.1.3](#)).

Analyses of change from Baseline to end of study in ALP and total bilirubin will be compared between treatment groups using analysis of covariance (ANCOVA) with change from Baseline as the dependent variable including treatment group and randomization stratification factor as fixed effects and the Baseline values as a covariate. The same analysis will be carried out using percentage change from Baseline as the dependent variable.

Descriptive statistics of the laboratory values will be summarized by treatment group. The results, change from Baseline, and percentage change from Baseline values as well as estimates of least-square means, standard errors, and 95% CIs will be presented by treatment group. Estimates of the mean difference between treatment groups, the standard error of the difference, and 95% CI of the difference will be presented.

13.1.5. Additional Secondary Efficacy Analyses

The following time to event secondary efficacy analyses will compare randomized OCA versus randomized placebo using the ITT population:

- Time to each component of the primary efficacy endpoint (except MELD score ≥ 15 which is captured above)
- Time to development of varix/varices
- Time to liver-related death
- Time to liver-related death or liver transplant
- Time to liver-related death, liver transplant, or MELD score ≥ 15

The same analysis methodology as used for the primary efficacy analysis will be used for these secondary efficacy analyses. Similar endpoints, where available, will be analyzed to compare OCA to historical controls as described below in [Section 13.1.8](#).

Analyses of changes in liver biochemistry (GGT, ALT, AST, conjugated bilirubin, albumin, and INR) will be summarized and analyzed using the same methodology as specified in [Section 13.1.4](#) for the key secondary analyses of change in ALP and total bilirubin.

Analyses of changes in MELD score, Child-Pugh score, Mayo Risk Score (MRS), IgM, CRP, TNF- α , FGF-19, CK-18, C4, and ELF score will be summarized and analyzed using the Wilcoxon Rank Sum Test to compare treatment groups. The median differences and 95% CI of the median differences between treatment groups will be constructed using Hodges-Lehmann estimate. If the median differences between treatments are not symmetrical around the median, the Sign Test may be used.

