9.4. Randomization and Blinding

This study will be conducted in a double-blind, placebo-controlled manner. Allocation to one of two treatment groups (OCA or placebo) will occur on a 1:1 ratio across sites and will be stratified by UDCA treatment (yes/no) and mean baseline bilirubin categories ($>ULN/\leq ULN$), as specified by the central laboratory. The randomization will be based on a predefined randomization code (generated by the Sponsor or designee) using an interactive web response system (IWRS), which the Sponsor intends will serve as a computer-based subject registration system at Screening and Day 0. The IWRS will serve as an investigational product inventory and management system and may be integrated with the study database.

The Investigator or designee will be required to register the subject in the IWRS and may be prompted to provide subject data necessary to properly randomize and allocate the subject to treatment. A randomization number will be assigned (refer to [Section 9.5.2](#), below) and investigational product dispensing information (ie, bottle number[s]) will be provided.

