13.1.3. Primary Efficacy Analysis

The primary efficacy endpoint will be the time to first occurrence of one of the following post-randomization:

- Death (all-cause)
- Liver transplant
- MELD score ≥ 15
- Hospitalization (as defined by a stay of 24 hours or greater) for new onset or recurrence of:
 - Variceal bleed
 - Encephalopathy (as defined by a West Haven score of ≥ 2)
 - Spontaneous bacterial peritonitis (confirmed by diagnostic paracentesis)
- Uncontrolled ascites (diuretic resistant ascites requiring therapeutic paracentesis at a frequency of at least twice in a month).
- Hepatocellular carcinoma confirmed by 2 complimentary imaging modalities.

The primary efficacy analysis will compare randomized OCA to randomized placebo with respect to the primary efficacy endpoint using the ITT population. Only adjudicated events will be included in analyses. The 2 treatment groups will be compared using the log rank test stratified by the randomization stratification factor. Kaplan-Meier (KM) estimates of the distribution of the time-to-event will be tabulated and graphed by treatment group. The tabulation will include the KM estimate of the medians and corresponding 95% confidence intervals (CIs), if the medians can be estimated. The number and percent of subjects censored and with events will be presented. The hazard ratio and 95% CI will be determined based on a Cox regression model stratified by randomization strata to estimate the magnitude of the effect.

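### The optional Sign Test fallback in Protocol 13.1.5 cannot compare two unpaired arms, and the rank-sum test it would replace is not stated to use the randomization strata; only exploratory comparisons are affected

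*Protocol*

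**What the plan says.** Protocol 13.1.5 covers change in MELD, Child-Pugh, Mayo Risk Score, IgM, CRP, TNF-alpha, FGF-19, CK-18, C4 and ELF. These are to be "summarized and analyzed using the Wilcoxon Rank Sum Test to compare treatment groups". On estimation: "The median differences and 95% CI of the median differences between treatment groups will be constructed using Hodges-Lehmann estimate". The fallback follows directly: "If the median differences between treatments are not symmetrical around the median, the Sign Test may be used".

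On design, Protocol 9.4 states "Allocation to one of two treatment groups (OCA or placebo) will occur on a 1:1 ratio across sites", and adds that allocation "will be stratified by UDCA treatment (yes/no) and mean baseline bilirubin categories". Nothing in the protocol matches an OCA subject to a placebo subject.

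The stratification factor is carried into the other between-arm analyses. For the primary endpoint (13.1.3): "The 2 treatment groups will be compared using the log rank test stratified by the randomization stratification factor". The Cox model in the same section is stratified, the ANCOVA in 13.1.4 includes the factor as a fixed effect, and the Cochran-Mantel-Haenszel test in 13.1.6.1 is stratified by it. The rank-sum sentence in 13.1.5 does not mention it.

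Section 13.1.11 places every endpoint outside the gatekeeping sequence on a descriptive and exploratory footing. That includes all ten measures above.

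**The concern.** The Sign Test counts signs of one difference per subject or per matched pair. Two independent arms supply no such difference, so the test named as a fallback for comparing treatments is not defined for that purpose. Its trigger also belongs to another procedure: symmetry of differences is an assumption of the paired signed-rank test, and the rank-sum test does not need it. Because the wording is permissive and gives no criterion for asymmetry, the protocol leaves the choice of test open until the data have been seen.

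A second, smaller matter is consistency. Bilirubin category is a randomization stratum, and bilirubin is an input to the Child-Pugh and Mayo Risk Scores (9.7.4, 9.7.5), so the strata could be prognostic for some of these outcomes. Leaving them out of the rank test gives away precision that the design has already paid for.

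At stake is whether the reported p-values for these scores and markers address the treatment contrast. Effect on markers of inflammation and fibrosis against placebo is a stated secondary objective (6.2).

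**Working it through.** The protocol states no operating figure for these tests, so there is none to reproduce; the 121 events in 13.1.2 concern the primary endpoint only.

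**Inputs.** About 350 subjects allocated 1:1 (13.1.2) give 350/2 = 175 per arm. The level is taken as two-sided 5%. Shifts, drifts, stratum shares and stratum effects are assumptions, because the protocol gives none. Simulations used 4,000 trials per setting, with Monte Carlo standard error √(0.05×0.95/4000) ≈ 0.003 at the 5% level and √(0.78×0.22/4000) ≈ 0.007 at power 0.78.

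**Step 1: ways the Sign Test could be run.**

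(a) *Within the OCA arm, on change from baseline.* If changes are normal with mean drift d (in SD), the mean of z is (Φ(d) − 0.5)/(0.5/√175). For d = 0.2 this is (0.579 − 0.5)/0.0378 ≈ 2.10, and the chance of rejection is about Φ(2.10 − 1.96) ≈ 0.56. With both arms drifting equally by 0, 0.1, 0.2 and 0.3 SD, simulation gave rejection in 5%, 19%, 56% and 88% of trials. The test is detecting a real change over time and says nothing about OCA against placebo.

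(b) *On arbitrary OCA-placebo pairs.* With no arm difference, rejection was 0.046 to 0.052, so the level holds. For a shift of 0.3 SD, the chance that a pair difference is positive is Φ(0.3/√2) = 0.584. Mean z is 0.084/0.0378 ≈ 2.22 with SD 2√(0.584×0.416) ≈ 0.986, so power ≈ Φ((2.22 − 1.96)/0.986) ≈ 0.60. For the rank-sum test, mean z ≈ 0.3×√(175/2)×√(3/π) ≈ 2.74, so power ≈ Φ(0.78) ≈ 0.78. Simulation gave 0.60 and 0.78. For exponential data with shift 0.2 it gave 0.68 and 0.84. The result also changes with the pairing chosen.

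(c) *On all 175×175 = 30,625 between-arm differences, as if independent.* The nominal standard error of the proportion positive is 0.5/175 = 0.00286. The true null value is √(351/(12×30,625)) = 0.0309, about 10.8 times larger. Rejection under no difference is 2(1 − Φ(1.96/10.8)) ≈ 0.86; simulation gave 0.85 to 0.86. The protocol does not say the test would be run this way.

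None of the three is a sound substitute for the rank-sum test.

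**Step 2: the trigger.** If the two arms have the same distribution, OCA-minus-placebo differences are symmetric about zero, however skewed the changes are. Under a pure location shift they are symmetric about the shift. So in the population the stated condition is met only when the arms differ in shape, and even then the rank-sum test remains a valid test of equal distributions.

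**Step 3: strata.** Two factors at two levels give four strata. Assumed shares are 63%, 27%, 7% and 3% (UDCA 90/10, bilirubin above ULN 70/30), with an assumed treatment shift of 0.3 SD for power.

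| Bilirubin-stratum effect (SD) | Type I error, rank-sum | Type I error, van Elteren | Power, rank-sum | Power, van Elteren |
|---|---|---|---|---|
| 0 | 0.051 | 0.052 | 0.792 | 0.789 |
| 0.25 | 0.047 | 0.049 | 0.785 | 0.785 |
| 0.5 | 0.045 | 0.052 | 0.751 | 0.766 |
| 1.0 | 0.028 | 0.049 | 0.713 | 0.777 |

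The unstratified test never exceeds 5% beyond simulation error and becomes conservative as the strata become prognostic. The power difference is nil at 0 and 0.25 SD, 0.766 − 0.751 = 1.5 points at 0.5 SD, and 0.777 − 0.713 = 6.4 points at 1 SD.

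**The case against.** The case for leaving the text alone has four parts. The fallback is optional, and the planned comparison, the rank-sum test with a Hodges-Lehmann interval, is valid. The endpoints are exploratory. The section is silent on stratifying the rank test rather than ruling it out, and a SAP may supply that. The efficiency loss is trivial unless the strata strongly predict the change. All of this stands, and it limits the weight of the point. It does not rescue the Sign Test sentence: there the protocol is not silent but names a test that does not fit the design, and a SAP would have to follow it or contradict it.

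Three stronger readings are tempting, and the documents do not support them.

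- A reader might infer a large false-positive rate. If 60% of subjects in both arms worsened (assumed), a within-arm Sign Test with 175 subjects has mean z of 0.1/0.0378 ≈ 2.65 and SD 0.98, so it rejects about 76% of the time. But that is power against a null of no change, which is false in this scenario. It is not an error rate for the treatment comparison, and 13.1.5 speaks of differences between treatments, not of reporting a within-arm test as one.
- A reader might infer that skewed changes would set off the switch. Step 2 of the check shows otherwise: the condition concerns between-arm differences, and these are symmetric when the arms do not differ. The wording also only permits the switch.
- A reader might infer that the score and biomarker comparisons as a whole are invalid. Only the fallback is ill-defined; the rank-sum analysis is at worst conservative.

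**Conclusion.** The point holds in limited form. The Sign Test sentence is wrong as written, because the arms are unpaired and the symmetry condition is not one the rank-sum test needs. This conclusion rests on the design alone and on no assumed figure. If the test were run on arbitrary pairs, power would fall from about 0.78 to 0.60 under an assumed normal shift of 0.3 SD with 175 per arm; run within an arm, it would answer a different question.

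The absence of the strata from the rank-sum test is a matter of efficiency and consistency, not validity. It costs about 0 to 2 power points for assumed stratum effects of 0 to 0.5 SD and about 6 to 7 points at 1 SD, under assumed stratum shares.

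Only exploratory comparisons are affected. The primary analysis, the four key secondary analyses and the study-wise type I error are not. The correction is still worth making, since it is nearly free and an exploratory p-value should test the contrast it is reported for.

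**What to change.** In 13.1.5, delete the Sign Test sentence. Replace the rank-sum test with the van Elteren test, stratified by UDCA use and baseline bilirubin category. Give a correspondingly stratified Hodges-Lehmann estimate with its 95% CI. If the Hodges-Lehmann estimate stayed unstratified, test and interval would rest on different comparisons and could disagree. No symmetry condition is needed for the test.

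The cost is a small edit to one paragraph of 13.1.5 and routine programming. No new data are needed, and sample size and the testing sequence do not change.

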13.1.6. Exploratory Efficacy Analyses

13.1.6.1. Responder Analyses

The percentage of subjects with a decrease in ALP of $\geq 15\%$ and $\geq 40\%$ from Baseline will be summarized by treatment group. In addition, the percentage of subjects with $ALP \leq ULN$ will be summarized by treatment group.

The percentage of subjects that meet the criteria of a responder based on each of the definitions below will be summarized by treatment group. The response classification at baseline will also be included in the summary:

- $ALP \leq 3 \times ULN$ and $AST \leq 2 \times ULN$ and total bilirubin $\leq ULN$ (Corpechot 2008)
- $ALP \leq 1.5 \times ULN$ and $AST \leq 1.5 \times ULN$ and total bilirubin $\leq ULN$ (Corpechot 2011)
- $ALP \leq 1.67 \times ULN$ and total bilirubin $\leq ULN$ (Momah 2012)
- Normal bilirubin (values $\leq ULN$) and normal albumin (values \geq lower limit of normal) (Kuiper 2009)
- $ALP \leq 1.76 \times ULN$ (Kumagi 2010)

Responder analyses will compare treatment groups using a Cochran–Mantel–Haenszel test stratified by the randomization stratification factor. Missing values will be considered as a non-responder.

13.1.7. Pharmacoeconomic and Health Outcomes Endpoints

Sufficient data will be collected on resource utilization and quality of life to undertake cost-effectiveness analyses that are relevant to the major countries taking part in this study. Resource utilization data on hospitalizations, healthcare provider visits, and medications will be combined with appropriate national unit costs to calculate a cost per patient per year in the study.

Quality of life data from patient-reported outcomes measures will be combined with survival data to calculate quality adjusted time in the study per patient. Cost-effectiveness analyses will report the incremental cost per major clinical outcome averted, liver-related death averted, life-year gained and quality-adjusted life year gained, including OCA as part of usual care versus usual care without OCA. Analyses will be conducted within the study and using a lifetime perspective. A separate economic analysis plan will be prepared and reported separately from this protocol.

13.1.8. Supportive Analysis

Per the International Conference on Harmonisation (ICH) E10 guidance, “where no obvious single optimal external control exists, it may be advisable to study multiple external controls”. In order to address the risks associated with the inclusion of a long-term placebo arm, supportive analyses of the primary endpoint will compare clinical outcomes in the OCA treatment arm to historical controls.

In an attempt to avoid the inherent biases with historical controls and to maintain the integrity of this comparison, one can invoke matching methods to optimize comparability and find a historical control that is “similar” to a participating subject. The historical database control

should be as similar as possible to the study population and should have been exposed to a similar standard of care (see [Section 5.5.2.3](#)).

A propensity score can be used to reduce bias through matching, stratification, regression adjustment, or some combination. Propensity scores use information from a pool of patients who do not participate in the study (historical controls) to identify what would have happened to participating subjects in the absence of the treatment. By comparing how outcomes differ for treated subjects relative to historical controls, it is possible to estimate the effects of the treatment.

Although it might be relatively simple to assign a historical control based on a single observable characteristic, in practice, if the matching process is to successfully mitigate potential bias, it has to be done considering a full range of covariates across which the treatment and historical controls might differ. Although the results of using matching controls are conditional only on the observed covariates, if one has the ability to measure many of the covariates that are believed to be related to the treatment assignment, then one can be fairly confident that approximately unbiased estimates for the treatment effect can be obtained. Both UK-PBC Group and the Global PBC Study Group formally collect numerous covariates that could be used for propensity score estimation including standard of care, eg, UDCA.

Historical controls will be chosen based on the same inclusion/exclusion criteria where possible.

Propensity scores will be estimated using the available covariates that predict receiving the treatment. Only covariates and not outcome variables will be included in the propensity score estimation. Therefore, there is no chance of biasing results in favor of one treatment.

The covariates and factors collected in the historical databases will be specified in the SAP.

Propensity scores will be estimated first through a logistic regression model with treatment group as the dependent variable and the above covariates/factors as independent variables. Then the stratum boundaries are determined based on the propensity score values for both groups (OCA population and control [historical and randomized placebo]) combined or in the OCA population or historical control group alone. Based on recommendations in the literature, quintiles of the estimated propensity score from the combined group will be used to determine the stratum boundary cut-offs for the different strata.

Outcome events collected in the historical database are: death (liver-related and all-cause), liver transplant, hepatocellular carcinoma, and other. Other is defined as cirrhosis or decompensation such as ascites, variceal bleed, and encephalopathy.

The propensity score quintile will be then be used as the stratification factor in the stratified log rank test to compare randomized OCA-treated subjects in the ITT population and historical controls (Overall Historical Control Population: both the UK-PBC Group and Global PBC Study Group databases) on the following outcomes:

- Time to death (all-cause)
- Time to liver-related death
- Time to liver transplant
- Time to liver transplant or death (all-cause)

- Time to liver transplant or liver-related death
- Time to hepatocellular carcinoma

KM estimates of the distribution of the time-to-event will be tabulated and graphed by treatment group. The tabulation will include the KM estimate of the medians and corresponding 95% CIs if the medians can be estimated. The number and percent of subjects censored and with events will be presented. The hazard ratio and 95% CI will be determined based on a Cox regression model stratified by randomization strata to estimate the magnitude of the effect.

Sensitivity analyses will be conducted limiting to the separate individual historical control databases, ie, UK-PBC Group and Global PBC Study Group. To evaluate the robustness of the propensity score estimations, additional algorithms and factors may be considered.

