8.3. Subject Exclusion Criteria

1. History or presence of other concomitant liver diseases including:
 - Hepatitis C virus infection
 - Active hepatitis B infection; however, subjects who have seroconverted (hepatitis B surface antigen and hepatitis B e antigen negative) may be included in this study after consultation with the medical monitor.
 - Primary sclerosing cholangitis
 - Alcoholic liver disease
 - Definite autoimmune liver disease or overlap hepatitis
 - Nonalcoholic steatohepatitis
 - Gilbert's Syndrome
2. Presence of clinical complications of PBC or clinically significant hepatic decompensation, including:
 - History of liver transplant, current placement on a liver transplant list, or current MELD score >12. Subjects who are placed on a transplant list despite a relatively early disease stage (for example per regional guidelines) may be eligible as long as they do not meet any of the other exclusion criteria.
 - Cirrhosis with complications, including history (within the past 12 months) or presence of:
 - Variceal bleed
 - Uncontrolled ascites
 - Encephalopathy
 - Spontaneous bacterial peritonitis
 - Known or suspected hepatocellular carcinoma
 - Prior transjugular intrahepatic portosystemic shunt procedure
 - Hepatorenal syndrome (type I or II) or Screening (visit 1 or 2) serum creatinine >2 mg/dL (178 µmol/L)
3. Mean total bilirubin >3× ULN

4. Subjects who have undergone gastric bypass procedures (gastric lap band is acceptable) or ileal resection or plan to undergo either of these procedures.
5. Other medical conditions that may diminish life expectancy, including known cancers (except carcinomas *in situ* or other stable, relatively benign conditions such as chronic lymphatic leukemia).
6. If female: plans to become pregnant, known pregnancy or a positive urine pregnancy test (confirmed by a positive serum pregnancy test by the central laboratory), or lactating.
7. Known history of human immunodeficiency virus infection.
8. Medical conditions that may cause non-hepatic increases in ALP (eg, Paget's disease or fractures within 3 months).
9. Other clinically significant medical conditions that are not well controlled or for which medication needs are anticipated to change during the study.
10. History of alcohol abuse or other substance abuse within 1 year prior to Day 0.

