13.1. Efficacy Analysis

13.1.1. Analysis Populations

The following subject populations will be evaluated and used for presentation and analysis of the data:

- The Randomized Population will include all randomized subjects.
- The Intent-to-Treat (ITT) Population will include all randomized subjects who receive any amount of investigational product (OCA or placebo). The ITT Population will be the primary population used for efficacy analyses. Treatment assignment will be based on the randomized treatment.
- The Safety Population will include all subjects who received any amount of investigational product (placebo or OCA). The Safety Population will be the primary population used for safety analyses. Treatment assignment will be based on the treatment actually received.
- The PK population will include all OCA subjects who have at least one confirmed fasted analyzable sample. Subjects must have been fasting for approximately 8 hours prior to the visit and must not have any major protocol deviations that potentially affect exposure levels. The PK population will be used for OCA PK analyses.
- The Overall Historical Control Population will include subjects from the United Kingdom (UK) -PBC Group and Global PBC Study Group databases with demonstrated comparability to randomized subjects in this clinical study (747-302) with respect to both subject characteristics and disease progression.
- The UK-PBC Historical Control Population will include subjects from the UK-PBC Group databases with demonstrated comparability to randomized subjects in this clinical study (747-302) with respect to both subject characteristics and disease progression.
- The Global PBC Historical Control Population will include subjects from the Global PBC Study Group database with demonstrated comparability to randomized subjects in this clinical study (747-302) with respect to both subject characteristics and disease progression.

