13.1.9. Alternative Primary Analysis

Based on sample size re-estimations, it may be determined that subjects will be enrolled to receive open-label OCA from that point forward, and the new primary efficacy analysis will become the comparison of all subjects in OCA population, to all control subjects (randomized placebo and historical controls) on time to liver transplant or death (all-cause) (see [Section 13.1.2.1](#)). Similar statistical methodology as specified above in [Section 13.1.8](#) for supportive analyses will be utilized.

The propensity score quintile will be then be used as the stratification factor in the stratified log rank test to compare groups. KM estimates of the distribution of the time-to-event will be tabulated and graphed by treatment group. The tabulation will include the KM estimate of the medians and corresponding 95% CIs if the medians can be estimated. The number and percent of subjects censored and with events will be presented. The hazard ratio and 95% CI will be determined based on a Cox regression model stratified by randomization strata to estimate the magnitude of the effect.

In addition, the outcome events specified above in Section 13.1.8 will also be evaluated to compare all subjects in OCA population to all control subjects (randomized placebo and historical controls).

Sensitivity analyses will be conducted limiting to the separate individual historical control databases, ie, UK-PBC Group and Global PBC Study Group. To evaluate the robustness of the propensity score estimations, additional algorithms and factors may be considered.

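### Section 13.1.8 says the registry comparison cannot be biased; it can, and no placebo-versus-registry comparison is specified to gauge by how much

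*Protocol*

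**What the plan says.** All references are to the Protocol.

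- **13.1.8, the score.** It is a logistic model for treatment group. "Only covariates and not outcome variables will be included in the propensity score estimation". The next sentence draws the conclusion: "Therefore, there is no chance of biasing results in favor of one treatment".
- **13.1.8, earlier in the section.** It acknowledges inherent biases with historical controls, concedes a limit ("Although the results of using matching controls are conditional only on the observed covariates"), and promises approximately unbiased estimates if many relevant covariates are measured.
- **13.1.8, selection of controls.** "Historical controls will be chosen based on the same inclusion/exclusion criteria where possible".
- **8.3.** The trial's own exclusions include "History of liver transplant, current placement on a liver transplant list, or current MELD score >12" and "Other medical conditions that may diminish life expectancy, including known cancers", as well as poorly controlled conditions, recent alcohol or substance abuse, and doubtful compliance.
- **13.1.1.** The historical populations must have demonstrated "comparability to randomized subjects in this clinical study (747-302) with respect to both subject characteristics and disease progression". No method or criterion is given.
- **13.1.8 and 13.1.9, comparisons listed.** Section 13.1.8 compares randomized OCA with the registries. Section 13.1.9, if triggered, compares all OCA subjects with "all control subjects (randomized placebo and historical controls) on time to liver transplant or death (all-cause"). Neither lists placebo against the registries. The sensitivity analyses take each database separately or vary the propensity algorithm and factors.

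**The concern.** Keeping outcomes out of the score stops anyone tuning the score to the results. It does nothing about prognostic differences that the score cannot see. An exclusion that is not applied in the registry, and whose marker is not recorded there, is such a difference. The listed exclusions mostly remove patients at higher risk of death or transplant, and those are the outcomes on which OCA and the registries are compared.

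At stake is how an OCA-versus-registry result is read. With large registries the standard error is driven mainly by the number of OCA events, so a modest residual difference in hazard can look like a drug effect. The text tells the reader that this cannot happen. In 13.1.8 the analysis is supportive, but similar methodology becomes the primary analysis if 13.1.9 is triggered. Section 5.5.2.3 also offers the historical comparison as help where the placebo arm is itself in doubt, for example because of commercial OCA.

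**Working it through.** **1. The passages side by side.** Section 13.1.8 says that estimates are conditional on observed covariates and at best approximately unbiased. The same section then says that bias in favour of one treatment is impossible. The only reason given for the second statement is that outcomes are not in the score, which bears on outcome-driven modelling and not on unmeasured confounding. The two statements cannot both stand.

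**2. The plan's own figure.** The only planning figure is for the randomized comparison (13.1.2): 4 × (1.960 + 0.842)² / (ln 0.60)² = 120.3, so 121 events, as stated. The plan gives no figure for the historical comparison, so its size can only be illustrated.

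**3. Illustration for 13.1.8.** Taken from the plan: 350 subjects at 1:1, so 175 on OCA; exponential survival; 2 years of accrual and 6 of follow-up, so follow-up uniform on 6 to 8 years; two-sided 5%, so 2.5% in favour of OCA. Assumed, not in the documents: 8-year transplant-free survival of 0.70, 500 to 3000 selected controls, no loss to follow-up, an inactive drug, and a registry hazard x times the trial hazard after adjustment.

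- Hazard: λ = −ln(0.70)/8 = 0.04458 per year.
- Event probability: p(λ) = 1 − [exp(−6λ) − exp(−8λ)]/(2λ) = 0.268, so OCA events = 175 × 0.268 = 46.9.
- With 1000 controls and x = 1.2: p(1.2λ) = 0.312, so 312 control events.
- SE of log HR = √(1/46.9 + 1/312) = 0.157.
- Expected apparent HR = 1/1.2 = 0.83. Mean shift = ln(1.2)/0.157 = 1.16 SE.
- P(significant in favour of OCA) = Φ(1.16 − 1.96) = 21.3%.

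| Residual excess registry hazard | 500 controls | 1000 controls | 3000 controls |
|---|---|---|---|
| 10% | 8.2% | 8.8% | 9.3% |
| 20% | 19.3% | 21.3% | 22.9% |
| 30% | 35.5% | 39.0% | 41.9% |

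**4. Direction.** A second model lets a share of controls carry an unapplied factor, using the plan's composite placebo hazard (survival 0.5 at 8 years) and a null drug. With 10% to 30% of controls at 2 to 4 times the hazard, the apparent HR runs from 0.93 down to 0.66. If the factor instead halves the hazard, it runs from 1.06 to 1.20, against OCA. The sign depends on which factors go unapplied or unmeasured.

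**5. What a placebo-versus-registry run would deliver.** The placebo arm also has 175 subjects and, with an inactive drug, the same hazard as OCA, so the SE is the same: about 0.15 to 0.17 at survival 0.70, and about 0.12 at the low end if survival is 0.50. With 1000 controls and x = 1.2, the 95% limits lie a factor exp(1.96 × 0.157) = 1.36 either side of the estimate. Used as a significance test, it would detect the bias only as often as the table shows.

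**The case against.** In context the sentence can be read as a point about outcome-blind design, and 13.1.8 names the inherent biases openly. That explains the sentence but does not rescue its wording.

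Several stronger readings are tempting, and the documents do not support them:

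- **That the registry benchmark is sicker.** The text says only that criteria are applied where possible. It does not say which ones fail, and 13.1.1.1 describes detailed subject-level data. Transplant listing is a recorded status, and 8.3 lets some listed subjects enrol. Step 4 shows that the bias can go either way.
- **That placebo is never compared with the registries.** Section 13.1.1 requires demonstrated comparability to randomized subjects, and those include placebo. What is missing is any stated method, and any placebo-versus-historical outcome analysis.
- **That nothing in the plan would reveal a problem.** Sections 13.1.4 and 13.1.5 give randomized OCA-versus-placebo hazard ratios on overlapping endpoints, including transplant or death. Set beside the registry results, these allow a crude check.
- **That false-positive rates could exceed 50%.** Such figures need 8-year survival of 0.50, which is the plan's assumption for the composite with MELD and decompensation, not for transplant or death.
- **That OCA versus registry should be read only relative to placebo versus registry.** This largely returns the randomized contrast and defeats the purpose stated in 5.5.2.3.

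Three further objections stand. Placebo subjects may start commercial OCA and remain in follow-up (9.2.1), so their hazard ratio against the registries need not be near 1 even with a sound benchmark. The nominal 2.5% does not formally govern 13.1.8, because 13.1.11 treats endpoints outside the hierarchy as exploratory. Section 13.1.9 is contingent, and 13.1.2.1 requires a protocol amendment for any change in allocation, so pooling rules could still be set then.

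**Conclusion.** The concern holds in limited form. The no-bias sentence is wrong and contradicts its own section. Residual bias remains from unrecorded factors and from criteria applied only where possible. It plausibly favours OCA, because the exclusions mostly remove high-risk patients, but the documents do not establish that. No placebo-versus-historical analysis is specified, although comparability must be demonstrated and 13.1.9 would pool the two groups for a primary analysis.

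The rates in the table are an illustration for 13.1.8 only. They rest on assumed survival of 0.70 and on an excess hazard taken to be what is left after propensity adjustment. They do not describe 13.1.9, which adds placebo to the controls and open-label subjects to OCA. The stakes are modest while the analysis is supportive, and highest if 13.1.9 is triggered.

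**What to change.** 1. In 13.1.8, replace the sentence with a statement that leaving outcomes out prevents tuning the score to the results, but does not remove bias from unrecorded factors or from trial criteria that could not be applied.
2. Add to 13.1.8, and as a step before any pooling in 13.1.9, the same propensity-quintile comparison of randomized placebo with the historical controls on the same outcomes. Take its hazard ratio from a Cox model stratified by quintile. As written, the section stratifies the test by quintile but the Cox model by randomization strata, which would leave the ratio unadjusted for the score.
3. Report that hazard ratio and its 95% CI beside the OCA-versus-historical result as a descriptive calibration, neither a pass/fail test nor a mandatory divisor.
4. State its limits: low precision (SE of log HR about 0.12 to 0.17 under the assumed rates), placebo subjects who start commercial OCA, and possibly informative censoring in any version that censors them at that point.

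The cost is protocol or SAP wording and one more run of code already planned. No new data are needed.
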